## **Quantitative Data Collection:**

Survey and urine pregnancy test data (from wives) will be collected from all enrolled couples in the CHARM2 RCT evaluation study. Both intervention and SOC arm participants will provide survey data at baseline and 9 & 18 month follow-ups. Survey data will be collected electronically on tablets using a unique identifier to link data between couples and across time. Wives in both the intervention and the SOC arms will be tested for pregnancy using a urine specimen at baseline and at both post-test timepoints; these data will directly be entered into the password protected electronic survey system at the time of survey data collection. Urine samples for pregnancy testing will not be retained for the study, but will be disposed of in disposal facilities upon completion of the test. Survey and pregnancy test results data will be stored locally on the tablet and, when internet is available, uploaded to the password-protected server. Separately, a list of contact names with unique identifiers will be maintained for tracking purposes; a hard copy form of this list will be kept in a locked file in [name] locked office at NIRRH. Baseline and follow-up surveys will be collected from couples using measures from the original CHARM study, which was based on India's Demographic and Health Survey (DHS/India's NFHS-3) and other validated measures. Couples must meet the eligibility criteria outlined below.

Eligible couples will be:

- Young wives (aged 18-29 years) and their husbands
- couples fluent in Marathi and both willing to participate
- no sterilization or infertility indicated (infertility is defined as having no pregnancy for 1+ years despite non-use of traditional or modern contraception)
- no pregnancy or female/male surgical sterilization planned for the next 18 months, and no reported use of consistent use of modern contraceptives in the past three months, and
- residing in the village for at least 2 years and residing together for at least 3 months, to facilitate follow-up tracking

The primary analyses will use an intent-to-treat approach and analyze all subjects according to randomized group. For subjects missing month 9 or 18 endpoints, these will be multiply imputed from the lower (worse) half of the distribution from their arm (conservative approach). Additional analyses will be conducted using a per protocol approach that includes only those subjects who complete the full intervention. Analyses will use women's data only; however, men's data will be used to validate outcomes a) increased contraceptive use, and b) reduced unintended pregnancy. Exploratory analyses using outcomes of contraception by type (e.g., LARC) may be conducted if numbers are sufficient across time-points.

At 18 month follow-up, healthcare facilities in the study area will be surveyed to assess provision of FP counseling and methods, availability of FP methods, approximate FP method client volume, provider type/qualifications, and participation in the CHARM2 intervention. Healthcare facility location GPS will be collected for mapping of healthcare services in the study area; no personally identifying information regarding the providers will be collected.

At 18 month follow-up, participants' location data will be re-collected in the form of GPS coordinates; this data will be used to examine distances to healthcare facilities in the study area. GPS data will be collected in a separate survey form to be accessed only by NIRRH in-country study staff. In-country study staff may use this location data, in conjunction with healthcare facility location data, to calculate participant-level distance to healthcare providers. Geolocation data will **not** be shared with UCSD or any other external sources; any maps produced which visualize healthcare facility location and access will **not** include participant locations. Calculated distances **only** may be shared with UCSD analysts, to be summarized and utilized in adjusted regression models to better understand drivers of and barriers to health care services generally, and family planning services specifically, in the study area.

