
## **6. SPECIFIC AIMS**

1) To implement the CHARM 2 GE+FP intervention, comprised of CHARM sessions with men and parallel sessions with women, and inclusive of broader contraceptive options including LARC, as well as one combined couples session. Men's sessions will be delivered by male health providers; women's sessions will be delivered by public Auxiliary Nurse and Midwives (ANMs), or a trained provider/counselor. The couple's session will be delivered by an ANM, trained provider, or counselor.

2) To evaluate the impact of CHARM2 on spacing contraceptive use (including LARC), unintended pregnancy, and MSV via a two armed cluster RCT with N=1200 married couples from 20 geographic clusters (n=60 couples per cluster) in rural India. The control arm will receive SOC in the form of community health workers offering pills/condoms and linking women to public health clinics. Outcomes will be assessed via pregnancy testing and surveys at baseline, 9 and 18-month follow-ups.

**Hypotheses:** We hypothesize that CHARM2 participants will be more likely than SOC participants to:

- a) Use contraception (including LARC) at 9 & 18-month follow-ups; effects on LARC will be explored
- b) Be less likely to report marital sexual violence (MSV) at 9 & 18-month follow-ups
- c) Not have an unintended pregnancy over the 18-month follow-up period.

3) To assess the quality, scalability, and replicability of CHARM2 for uptake by rural health systems (i.e., sustainability), using implementation science methods including IDI with CHARM2 couples (n=50) and providers (n=20), 5-7 focus groups with MILs of couples that participate in IDIs, control condition couples (n=20), and key stakeholders from the FP and rural health infrastructures at state, national and international levels (n=50), survey of healthcare facilities in the study area (n approximately=250), and a cost-effectiveness analysis.

Should CHARM2 prove effective and sustainable, study findings will have broad implications for FP interventions for low resource settings in India and elsewhere.

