**Data Analysis:** The primary comparison of the binary outcomes between intervention groups at 9 & 18-months will use mixed-effects longitudinal logistic regression, with random effects for the individual (couple) and for geographical clusters, over time. Baseline will be included as a time point (Aims 2a, 2b only). A categorical time effect will be used (profile model). A “difference-in-differences” analysis will compare the treatment arms. Statistically, this amounts to testing for an interaction between time and treatment arm in the longitudinal model. In addition, the intervention groups will be compared via a generalized estimating equations (GEE) logistic regression analysis. The GEE models will use a nested exchangeable working correlation matrix that takes into account geographic clusters and the individual (couple) within the cluster. No other covariates will be included in the primary analysis. Since the treatment assignment is at random this “un- adjusted” analysis will provide a causal effect of the intervention. However, we will also conduct secondary analyses, adjusting for potentially relevant covariates (e.g., age, current pregnancy, past year child- birth, etc.), in addition to time and treatment arm, using backward model selection at the  $\alpha=0.15$  threshold level. These secondary analyses may improve precision (power) of estimating the treatment effect and reduce any bias due to random imbalances between arms.

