
**Cost Effectiveness:** To further inform utility of CHARM2, a cost-effectiveness analysis will be conducted under the direction of [name] using WHO-CHOICE methodology, an internationally accepted standard of economic analysis of health programs. Costs will be collected prospectively and include capital costs (e.g., equipment, space) and recurrent inputs (e.g., FP supplies, administrative costs). Given an expected outcome of improved contraception, costs of increases in non-CHARM2 FP services will be included as partner costs. Costs will be discounted at a rate of 3% per year, per WHO-CHOICE recommendations, varying from 0% to 6% in the sensitivity analysis. Drivers of variation in the total program cost will be assessed using multivariate linear regression. Cost-effectiveness will be calculated by dividing the total program costs by total health outcomes achieved over intervention duration. Outcome measures will include number reached by the CHARM2 and unintended births averted (based on outcome analyses). Based on prior research, we will use an estimate of 3.8 DALYs averted per unintended birth averted. We will also include quantitative measurements of other benefits from unintended pregnancy prevention (e.g., household savings and assets) to capture some of the spill over effects of when unintended pregnancies are prevented. Following WHO benchmarks, the intervention will be categorized as ‘very cost-effective’ if the cost per DALY averted is  $<1x$  the country’s per capita GDP. We will undertake a probabilistic sensitivity analysis, sampling each cost and outcome from an appropriate distribution to determine mean incremental cost-effectiveness, and assess drivers of uncertainty using ANCOVA. Findings will be used to support sustainability and scale up of CHARM2 for use in rural India and elsewhere.

**Sample size considerations:** Treatment effects detectable with 80% power given the 2-armed design with 20 clusters of 48 measurable couples (assuming 80% retention) per arm, or n=960 observed couples. Power calculations took into account multiple levels of clustering, both within-village and within-sub center variance.

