- a) Based on CHARM, we expect the proportion of women using modern contraception in the control group to be 40% at 18 month follow-up. This study will have 83.3% power to detect an absolute difference of 12% or more between treatment groups at follow-up, or 40% vs 52% in the two groups, with total kappa [variance]=0.10, assumed to be split equally between within-village variance and within-cluster variance . These values were found in the CHARM study.
- b) Based on CHARM, we expect that 89.2% of women in the control group will report no recent MSV at 18 month follow-up. We have 91.5% power to detect an absolute difference of 6% or more between treatment groups (89.2% vs. 95.2%) with kappa=0.036,

assumed to be split equally between within-village variance and within-cluster variance. The effect size of 6% difference and the kappa=0.036 were observed in the CHARM study.

c) Based on CHARM, we expect the proportion of women with no unintended pregnancy over 18 month follow-up to be 90% in the control group. This study will have 89.5% power to detect an absolute difference of 5.5% or more between groups (90% vs. 95.5%), with kappa=0. The effect size of 5.5% difference is based on a meta-analysis of cluster RCTs evaluating impact of FP interventions on unintended pregnancy (with comparable measures to this study). The study showed a 50% reduced risk for intervention participants with no unintended pregnancy in the CHARM group, or 5.5%. The kappa=0 is based on the CHARM study, where no significant intra-cluster correlation was found for this outcome.

While we will use longitudinal mixed effects logistic regression methods in our analyses, for power calculations we considered only the 18-month time point in a model similar to those to be used in the analyses. Power for the prescribed longitudinal analyses will be higher. Power calculations for each hypothesis used statistical simulations with 10,000 iterations. The conversion from kappa to the random cluster effect was done using the delta method, and was confirmed through the simulation.

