## **14. POTENTIAL RISKS**

Questions included in qualitative and quantitative assessments with men and women may be embarrassing or emotionally upsetting to participants as they assess sexual and contraceptive behaviors, and for women, physical and sexual violence from husbands. Embarrassment is reduced by the brevity of the research tools and the use of matched-gender and well-trained research interviewers. Also, assessments of abusive or controlling behavior from husbands are asked of wives confidentially, and not from husbands. Wives and husbands will be recruited from the same households, but in accordance with the World Health Organization's "Ethical and Safety Recommendations for Research on Domestic Violence Against Women", only wives will be assessed for domestic violence. These recommendations guide against asking husbands about perpetration or informing husbands of what wives are being asked, to reduce risk for violence. Husbands will be asked about their attitudes toward domestic violence, including marital sexual violence (MSV), a targeted outcome of the CHARM2 intervention. Wives will be asked about their marital sexual experiences including MSV as part of intervention sessions with ANMs or trained providers/counselors; again, this can create discomfort or potential vulnerability to violence if the husband learns of this disclosure. Wives will be discouraged from sharing both the nature of the questions and their responses in surveys and intervention sessions, with their husbands or others, and researchers will not share this information with husbands. To further protect wives, we will follow protocols used in our prior intervention studies on domestic and sexual violence to reduce risk for wives; these protocols are consistent with the World Health Organization's "Ethical and Safety Recommendations for Research on Domestic Violence Against Women."

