## **15. RISK MANAGEMENT PROCEDURES AND ADEQUACY OF RESOURCES**

In addition to the protections against risks briefly outlined in the Potential Risks section above, additional precautions have been outlined to reduce risk for violence to wives, given the vulnerability of this population. These protocols and procedures were developed based on WHO guidelines for domestic violence research, and based on existing NIH-funded projects Drs. [name] and [name] have or have had in both India and the US. These protocols include (but are not limited to) the following efforts:

If women at any point in the study report life-threatening violence from husbands, these women will be withdrawn from the study and provided with supported referral (assistance with transport and accompaniment) to a state domestic violence agency (CEHAT) by research or program staff. Research staff, ANMs, and trained providers/counselors will be trained on how to work with women in these situations in accordance with WHO guidelines for domestic violence research. For example, this includes using "dummy" questions if privacy is breached during an interview or an ANM or trained provider/counselor visit, and training staff to identify when women are distressed and need debriefing or immediate health attendance. They will also offer support to conduct a safety plan with woman reporting spousal violence to ensure she has thought through ways to safely escape her situation should she choose to do so.

Research and program staff will never disclose to any family member who participated in the study, what questions were asked of them, or what responses were given. Participants will also be asked not to share the questions and their responses with others, particularly if they think it could put them at risk for abuse. This is in line with WHO procedures for domestic violence research.

Women will always be assessed for domestic violence in private places, with clarification that women can refuse to respond to items or questions, with supported referral and safety planning for identified victims, with validation that violence is never a woman's fault, with protocols and confirmation that all information provided is kept confidential, and with emotional debriefing subsequent to disclosure, in line with WHO procedures for domestic violence research.

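### Imputing missing 9- and 18-month endpoints from the worse half of the couple's own arm is undefined for binary outcomes, is not reliably conservative, and can create a false effect when retention differs by arm

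*Combined protocol and SAP*

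**What the plan says.** The rule stands in section 9, Quantitative Data Collection, in the paragraph that sets the primary intention-to-treat analysis. For couples missing the month 9 or month 18 endpoint, "these will be multiply imputed from the lower (worse) half of the distribution from their arm (conservative approach").

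The Data Analysis paragraph of section 9 shows which variables this governs: "The primary comparison of the binary outcomes between intervention groups at 9 & 18-months will use mixed-effects longitudinal logistic regression". It adds that "the intervention groups will be compared via a generalized estimating equations (GEE) logistic regression analysis". The Sample size considerations paragraph expects one couple in five to be lost: "20 clusters of 48 measurable couples (assuming 80% retention) per arm, or n=960 observed couples".

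The plan does not define the worse half of a yes/no outcome. It gives no imputation model or number of imputations, and does not say how cluster or earlier visits enter. It names no sensitivity analysis for missing data; the only alternative beside the rule is a per-protocol analysis, which answers a different question.

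**The concern.** There are three difficulties.

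- **The rule cannot be carried out as written.** A 0/1 variable has no natural lower half, so the analyst must choose a meaning, possibly after seeing the data. Reasonable choices move the contraception result in opposite directions.
- **The conservative label is not earned.** Each arm is penalised from its own distribution, so the arms are not pulled together. Conservatism towards the null would require the intervention arm's missing couples to lose their assumed benefit.
- **The penalty grows with the share missing.** If one arm keeps more couples, it is penalised less, and retention alone produces a treatment difference.

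The rule fixes the primary result for a planned fifth of the sample. Readers told it is conservative would trust a positive result that retention could have produced, or accept a null result caused the same way. If the imputed absolute difference also feeds the births-averted figure in the cost-effectiveness analysis (the plan does not say), that figure would be inflated too.

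**Working it through.** **Inputs.** Section 9 gives 1200 couples in 20 clusters of 60 and 80% retention; I take 10 clusters per arm, so 600 enrolled and 480 observed per arm. The planning rates are in the same section; for MSV, for example, "we expect that 89.2% of women in the control group will report no recent MSV at 18 month follow-up". As bad-outcome rates *q*, control versus CHARM2, they are 60% vs 48% (non-use of contraception), 10.8% vs 4.8% (MSV) and 10% vs 4.5% (unintended pregnancy). Two-sided alpha of 0.05 is my assumption.

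**The plan's own figure.** Power for unintended pregnancy (kappa = 0) is stated as 89.5%. With 480 per arm, the standard error is √(0.90×0.10/480 + 0.955×0.045/480) = 0.0166 and the pooled null standard error is 0.0167. So z = (0.055 − 1.96×0.0167)/0.0166 ≈ 1.33, and power is 90.9%; a cluster-level t test with 18 degrees of freedom gives 87.8%. The stated figure lies between these, so the inputs are read correctly.

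**Literal reading.** The worse half of an arm with bad rate *q* has bad rate min(1, 2*q*). With share *m* missing, and missing couples resembling observed ones, the arm's rate after imputation is (1−*m*)*q* + *m*·min(1, 2*q*), which equals *q*(1+*m*) when *q* < 0.5.

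**Equal retention, m = 0.20**

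| Outcome | Bad rates after imputation | Difference (points) | Log odds ratio |
|---|---|---|---|
| MSV | 12.96% vs 5.76% | 6.0 → 7.2 | 0.876 → 0.890 (+1.6%) |
| Unintended pregnancy | 12.0% vs 5.4% | 5.5 → 6.6 | 0.858 → 0.871 (+1.5%) |
| Contraception (non-use) | 68.0% vs 57.6% | 12.0 → 10.4 | 0.486 → 0.447 (−8%) |

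The risk ratios for MSV (0.44) and pregnancy (0.45) do not change. The pregnancy shift is smaller if a month-9 pregnancy already settles an outcome defined as "Not have an unintended pregnancy over the 18-month follow-up period". For contraception, every missing control couple is imputed as a failure (min(1, 1.2) = 1), so those imputations do not vary.

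**A milder reading.** Suppose the worse half has 1.25 to 1.5 times the arm's rate. Every difference is then multiplied by 1 + 0.20×0.25 = 1.05 to 1 + 0.20×0.5 = 1.10. Contraception becomes 12.6-13.2 points, MSV 6.3-6.6 and pregnancy 5.8-6.1. Contraception now moves away from the null, the opposite of the literal reading.

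**Unequal retention, no true effect.** The spurious difference is (m_control − m_CHARM2) × (worse-half rate − *q*), taken at the control rates. The plan gives no retention by arm, so the splits are assumptions.

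| Outcome | 25% vs 15% missing | Odds ratio | 22.5% vs 17.5% missing |
|---|---|---|---|
| Contraception | 0.10×0.40 = 4.0 points | 1.20 | 2.0 points |
| MSV | 0.10×0.108 = 1.1 | 1.10 | 0.5 |
| Unintended pregnancy | 0.10×0.10 = 1.0 | 1.10 | 0.5 |

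Reversing the split gives the same sizes against CHARM2.

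**Type I error by simulation.** The design was 10 clusters of 60 per arm with beta-binomial outcomes, 20 imputations combined by Rubin's rules, an 18-month marginal logistic contrast with cluster-robust variance and t(18), and 10,000 replicates per scenario. Kappa is not defined in the plan. Read as a coefficient of variation, it gives an intracluster correlation (ICC) of 0.10²×0.40/0.60 = 0.007 for contraception and 0.036²×0.892/0.108 = 0.011 for MSV. The stated 83.3% power for contraception implies roughly 0.010-0.014. Nominal level is 5%.

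| Outcome (ICC) | 25% vs 15% missing | 20% in both arms | Observed data only |
|---|---|---|---|
| Contraception (0.003-0.014) | 19-27% | about 5% | about 5% |
| MSV (0.005-0.036) | 7-13% | 6-11% | about 5% |
| Unintended pregnancy (0) | 6-9% | 5-6% | about 5% |

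If kappa meant an ICC of 0.05-0.10, contraception would be at 10-13%, but the design would then have only 32-54% power, which does not fit the stated figure. A separate simulation with a cluster-level t test (4,000 replicates, contraception coefficient of variation 0.10, no clustering for the other two) gave 23%, 9.0% and 9.2% at 25% vs 15%. In it, with the planned contraception effect and the split reversed, power fell from about 85% on observed data to 43%.

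**The case against.** The strongest reply is that the false-effect scenario is hypothetical. Nothing in the plan forecasts unequal retention; home visits and the residence criteria apply to both arms. The one arm-specific route in the documents combines "If women at any point in the study report life-threatening violence from husbands, these women will be withdrawn from the study" (section 15) with "Wives will be asked about their marital sexual experiences including MSV as part of intervention sessions with ANMs or trained providers/counselors" (section 14). It would remove more CHARM2 than control couples, so the retention penalty would fall on CHARM2. This is fair: the bias is conditional, can go either way, and is smaller with a smaller gap (at 22.5% vs 17.5%, about 9-10% type I error for contraception at an ICC of 0.01). For MSV itself, however, a CHARM2 woman withdrawn for violence would be imputed with only a 2×4.8% = 9.6% chance of MSV, which is hardly pessimistic.

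Other points also stand in part:

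- On the log-odds scale that the models test, the equal-retention change for MSV and pregnancy is negligible. The accurate statement is that the rule adds no conservatism there, not that it is seriously anti-conservative.
- Much of the MSV inflation appears with equal missingness too, and comes from imputing an arm-wide rate without regard to cluster. The plan does not say that cluster is ignored.
- The milder reading is one choice among several. A common odds shift of 1.5-3 gives 11.3-11.8 points for contraception and slightly smaller log odds ratios for all three outcomes. That the direction depends on the choice confirms that the rule is undefined.
- The simulations use one time point, not the longitudinal mixed model with its time-by-arm test, so the error rates are indicative.

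None of this supplies a definition or justifies the conservative label.

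**Conclusion.** The concern holds. The rule needs an unstated choice before it can be run. Under its literal reading and the plan's own rates and retention, it attenuates only contraception; MSV and pregnancy differences widen by a fifth in absolute terms and are essentially unchanged in log odds.

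Retention alone can produce a difference: 4.0, 1.1 and 1.0 points for contraception, MSV and pregnancy at an assumed 10-point gap, and about half that at 5 points, in favour of whichever arm keeps more couples. These sizes rest on the literal reading, on missing couples resembling observed ones, and on the assumed splits. The absence of a definition and the unsupported label rest on none of them. Because this is the primary analysis, it should be corrected before outcome data are examined.

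**What to change.** Remove the worse-half rule and the word conservative from the primary analysis.

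- **Mixed model:** use all observed data, valid under missing at random (MAR), or multiple imputation under MAR by arm, using the baseline value, the 9-month value and cluster.
- **GEE:** use those MAR imputations, because an unweighted GEE on observed data is not in general valid under MAR.
- **Sensitivity analysis 1:** impute missing CHARM2 couples from the control distribution. At 20% missing, each planned difference is multiplied by 0.8, giving 4.8 (MSV), 4.4 (pregnancy) and 9.6 points (contraception), so all three are attenuated.
- **Sensitivity analysis 2:** a tipping-point analysis with the shift varied separately by arm.
- **Reporting:** missingness by arm and reason, including violence-related withdrawal.

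Defining the worse half and keeping the rule would cure the ambiguity but not the dependence on retention. The drawback of the change is that the primary result rests on MAR, which violence-related withdrawal may breach for MSV; the tipping-point analysis addresses this. The cost is revised SAP wording, the MAR imputations and two sensitivity analyses, with no new data.
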